### 6.3.3 Safety/tolerability analysis

Since enrollment is concurrent with receiving the first vaccination, all participants will have received at least 1 vaccination and therefore will provide some safety data.

### 6.3.3.1 Reactogenicity

The number and percentage of participants experiencing each type of reactogenicity sign or symptom will be tabulated by severity and the percentages displayed graphically by arm. For a given sign or symptom, each participant's reactogenicity will be counted once under the maximum severity for all injection visits.

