## 9.8 Assessments of reactogenicity

For all participants, baseline assessments are performed before and reactogenicity assessments are performed after each vaccination. All reactogenicity symptoms are followed until resolution and graded according to the DAIDS Table for Grading the Severity of Adult and Pediatric Adverse Events, Corrected Version 2.1, July, 2017, except as noted in Section 11.2.2.

The reactogenicity assessment period is 7 full days following each vaccination per the assessment schedule shown in [Table 9-1](#). Participants are instructed to record symptoms using a Participant Diary. Contact between the participant and the site staff should take place at least once within 72 hours/3 days postvaccination. In general, a participant who self-reports any postvaccination reaction greater than mild is seen by a clinician within 48 hours after onset, unless the reaction is improving and/or has completely resolved. Clinic staff will follow new or unresolved reactogenicity symptoms present at day 7 to resolution. Participants are instructed to contact the clinic for events that arise during the period between vaccination and the next scheduled visit.

Reactogenicity events are reported using CRFs that correspond to the time of assessment in [Table 9-1](#). Reactogenicity assessments include assessments of systemic and local symptoms and vaccine-related lesions. Events not listed on a CRF, or with an onset after the reactogenicity assessment period (day of vaccination and 7 full days after), or those meeting SAE/AEs requiring expedited reporting to DAIDS criteria, are recorded on an adverse experience log form.

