**Table 9-1 Schedule of reactogenicity assessments**

Day	Time	Performed by
0 a	Baseline: before vaccination	HVTN CRS clinician
	Early: 25-60 minutes after vaccination	HVTN CRS clinician
	Between early assessment and 11:59pm day 0	HVTN CRS clinician or participant
1-7 b	Between 12:00am and 11:59pm on the respective day	HVTN CRS clinician or participant

a Day of vaccination

b New or unresolved reactogenicity symptoms present on day 7 are followed until resolution

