### 9.8.1 Assessment of systemic and local symptoms

Systemic symptoms include increased body temperature, malaise and/or fatigue, myalgia, headache, chills, arthralgia, and nausea. Local symptoms include pain and/or tenderness at the injection site. The daily maximum severity reached for each symptom during the assessment period is reported.

Body temperature is measured by oral or infrared thermometry. All temperatures must be measured by non-axillary thermometry. This includes temperatures taken in the clinic, as well as temperatures taken by participants during the reactogenicity period.

Temperature is reported in degrees Celsius. If temperature is measured in Fahrenheit, the conversion to Celsius should be documented in the participant's chart note. A measurement is taken once daily during the assessment period and should be repeated if participant is feeling feverish.

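### The Grade 1+ laboratory count and the maximum-severity reactogenicity table are not conditioned on the baseline or pre-dose grade, so unchanged findings (for example an eligible WBC of 2,500 to 2,999) are counted together with new ones

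*Combined protocol and SAP*

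**What the plan says.** **Reactogenicity.** Section 6.3.3.1 tabulates each sign or symptom by severity; a participant's "reactogenicity will be counted once under the maximum severity for all injection visits". The pre-dose grade is not mentioned. It is collected: under Section 9.8, "baseline assessments are performed before and reactogenicity assessments are performed after each vaccination". Table 9-1 has a row "Baseline: before vaccination", followed by an early reading, a reading for the rest of Day 0, and daily readings on Days 1 to 7. Section 9.8.1 adds: "The daily maximum severity reached for each symptom during the assessment period is reported". It sets no condition that the symptom be new or worse. The solicited systemic symptoms include fatigue, myalgia, headache and arthralgia.

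**Laboratory values.** Section 6.3.3.3 plans box plots that include baseline and summaries of change from baseline. It then plans the number and percentage of participants at Grade 1 or above at each postvaccination timepoint, with no reference to the grade at baseline. For grading it cites the DAIDS table through Section 9.8, which uses "Corrected Version 2.1, July, 2017, except as noted in Section 11.2.2". Section 11.2.2 grades all AEs with study-specific exceptions, and its Table 11-5 makes a WBC of 2,000 to 2,999 Grade 1.

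**Who may enter.** Section 7.1 (criterion 14) admits a WBC from 2,500 to 12,000. Section 7.2 (criterion 6) excludes a SELENA-SLEDAI score only when it is above 4.

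**Status.** Section 5.1 makes both reactogenicity and laboratory measures primary safety endpoints.

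**The concern.** People with quiescent SLE can have joint pain, fatigue or a low white cell count before they receive any vaccine. A count of postvaccination grades that ignores the starting grade adds those findings to the ones that appeared or worsened after a dose. With 16 participants and no concurrent control group, no other column in the table shows the background rate. A reader of the primary safety tables could not tell from these counts whether a Grade 1 WBC or a Grade 1 arthralgia was already there. Section 4.1.2 also plans to set safety outcomes beside those of healthy RV328 vaccinees. If reactogenicity or laboratory grades are part of that comparison, the mixing would make the SLE cohort look less tolerant of the vaccine than it is.

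**Working it through.** **1. The plan's own figure.** The documents give no figure on this point. The nearest safety figure is the Table 6-1 chance of at least one event among 16 at a true rate of 10%: 1 − 0.9^16 = 1 − 0.185 = 0.815, which reproduces. It does not bear on baseline.

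**2. WBC overlap.**
- Entry range (Section 7.1): 2,500 to 12,000.
- Grade 1 range (Table 11-5): 2,000 to 2,999.
- Intersection: 2,500 to 2,999. Every value here is both eligible and Grade 1.
- Under the unmodified DAIDS cut point, which Section 11.2.2 gives as 2,500, no eligible value falls below the cut point. The overlap comes from the study's own grading.

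**3. How often such a value is counted.** Appendix F schedules a CBC after Day 0 at visits 03 to 11 (nine) and 13 (one): 9 + 1 = 10. Check from Appendix E: 60 mL / 5 mL = 12 draws = screening + Day 0 + 10. Two of the ten (Days 28 and 168) are drawn before doses 2 and 3, but after dose 1. One participant can therefore appear in up to 10 timepoint columns. Each column has its own count; they do not accumulate.

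**4. Symptom route.** Appendix G gives arthritis, which by definition includes joint pain, a weight of 4. A score of 4 is not above 4, so arthritis alone passes criterion 6. If the joint pain continues at the same grade after the dose, Section 9.8.1 has it reported and Section 6.3.3.1 counts it.

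**5. Size.** One participant is 1/16 = 6.25 percentage points of a row, two are 12.5 and three are 18.75, if they are not otherwise counted there. The documents give no prevalence of pre-dose symptoms. As an assumed range, if 10%, 20% or 40% had a persistent symptom and the vaccine added nothing, the table would show on average 16 × 0.10 = 1.6, 16 × 0.20 = 3.2 or 16 × 0.40 = 6.4 participants with reactogenicity. An increase-over-pre-dose table would show 0.

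**6. How noisy an increase-over-pre-dose count is.** Table 9-1 gives one pre-dose reading per injection, by a clinician. After the dose there are 1 (early) + 1 (rest of Day 0) + 7 (Days 1 to 7) = 9 readings, of which 1 + 7 = 8 may be the participant's own. Over three injections that is 3 against 27. Assume no vaccine effect, a symptom of a single grade, and independent readings, each positive with probability p. The chance of an apparent increase at one or more injections is

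1 − [1 − (1 − p)(1 − (1 − p)^9)]^3

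- p = 0.01: 0.24
- p = 0.02: 0.41
- p = 0.05: 0.73

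If the symptom is constant within a person, the chance is 0. Real readings are probably correlated, so the truth lies between.

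**The case against.** The other side has several sound points.

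- **Pre-dose reading.** A reader might infer that the pre-dose reading itself enters the maximum, because it is a row of Table 9-1 and "Reactogenicity events are reported using CRFs that correspond to the time of assessment in" that table. The documents do not support this. Section 9.8 separates baseline from reactogenicity assessments and defines the reactogenicity period as following vaccination, and Section 9.8.1 takes its maxima within that period. Only persistence after the dose remains.
- **Grading version.** A reader might infer that the WBC grading is undetermined, since the sentence in Section 9.8 that carries the exception begins "All reactogenicity symptoms are followed until resolution and graded according to the DAIDS Table" and so speaks of symptoms. That is too strong. Section 6.3.3.3 refers to AE criteria, Section 11.2.2 covers all AEs, and it states the WBC table to be applied in this study. Table 11-5 is the natural reading. The 3,000 threshold was chosen deliberately to match SELENA-SLEDAI leukopenia. This settles the grading and leaves the baseline question open.
- **Other displays.** It would be wrong to say that the plan ignores baseline. Section 6.3.3.3 has baseline box plots and changes from baseline. Section 6.3.3.4 joins each participant's SELENA-SLEDAI values over time. Section 6.3.3.2 tabulates AEs by relationship. This is partial coverage: the SELENA-SLEDAI plot shows a total score, relationship is a judgment about cause, and none counts participants whose laboratory or symptom grade rose.
- **Safeguards.** Exclusion criterion 26 and the dose-delay provision in Section 7.3.1 may reduce the problem. They rest on judgment and are not analysis rules. CRF instructions and the Study Specific Procedures may hold a recording rule; they are not among the documents.
- **Direction.** Unadjusted counts over-report rather than hide a signal, and no pause rule in Table 11-8 uses them. This stands and limits the severity.
- **The remedy.** A bare count of participants who got worse carries no severity and is sensitive to fluctuation. The first fault is met by tabulating by severity; the second cannot be removed and must be stated.

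**Conclusion.** The point holds as a minor one, a cheap improvement. Two primary safety counts mix findings that were present and unchanged with findings that are new or worse, although the data to separate them are collected. For WBC this follows directly from the plan's own ranges: 2,500 to 2,999 is eligible and Grade 1, at up to 10 visits, given Table 11-5. For symptoms it rests on an assumption that some participants have a solicited symptom before a dose that continues unchanged.

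The size is up to 6.25 percentage points per affected participant per row. The number affected cannot be derived, so a reader should not infer that the reported rates will be inflated by any known amount. Nor should a reader infer a risk to safety monitoring: the effect is on reporting and leans toward over-reporting.

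**What to change.** Keep the existing tables and add two.

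- **Section 6.3.3.3:** a shift table from baseline grade to worst postvaccination grade for each laboratory measure, with a statement that grading is as modified in Section 11.2.2. Baseline is the last value before first vaccination: Day 0, or screening for ALT, because Appendix F has no chemistry panel on Day 0.
- **Section 6.3.3.1:** a table by severity. For each symptom, take the vaccinations at which the post-injection maximum exceeds the pre-injection grade at the same visit, and report the participant's highest post-injection grade among those. For example, someone with unchanged Grade 2 arthralgia at dose 1 and a rise from 0 to 1 at dose 2 stays under Grade 2 in the existing table and appears under Grade 1 in the new one. A short sentence confirming that the pre-dose row of Table 9-1 is outside the maximum would be a useful clarification.

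The cost is a few sentences and a little programming; no new data are needed. There are downsides to state with the tables:
- One pre-dose reading is set against nine post-dose readings, so fluctuation alone can show worsening. The laboratory shift table likewise sets one value against many.
- A true reaction no worse than the pre-dose grade appears only in the unadjusted table.
- The ALT baseline may be up to 28 days before enrollment.

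The added counts should be labelled descriptive and not vaccine-attributable.

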### 6.3.3.2 AEs and SAEs

AEs will be summarized using MedDRA System Organ Class and preferred terms. Tables will show the number and percentage of participants experiencing an AE within a System Organ Class or within preferred term category by severity or by relationship to study product. For the calculations in these tables, a participant with multiple AEs within a category will be counted once under the maximum severity or the strongest recorded causal relationship to study product.

A listing of SAEs reported to the DAIDS Regulatory Support Center (RSC) Safety Office will provide details of the events including severity, relationship to study product, time between onset and last vaccination, and number of vaccinations received.

### 6.3.3.3 Local laboratory values

Box plots of local laboratory values will be generated for baseline values and for values measured during the course of the study visit. Each box plot will show the first quartile, the median, and the third quartile. Outliers (values outside the box plot) will also be plotted. If appropriate, horizontal lines representing boundaries for abnormal values will be plotted.

For each local laboratory measure, summary statistics will be presented by study cohort and timepoint, as well as changes from baseline for postenrollment values. In addition, the number (percentage) of participants with local laboratory values recorded as meeting Grade 1 AE criteria or above as specified in the Division of AIDS (DAIDS) Table for Grading the Severity of Adult and Pediatric Adverse Events (Section 9.8) will be tabulated for each postvaccination timepoint. Reportable clinical laboratory abnormalities without an associated clinical diagnosis will also be included in the tabulation of AEs described above.

### 6.3.3.4 SELENA-SLEDAI

Box plots will be generated for baseline values and for values measured during the course of the study. Each box plot will show the first quartile, the median, and the third quartile. Outliers (values outside the box plot) will also be plotted. Each participant's points will be connected with a line. Summary statistics will be presented by study cohort and timepoint. A listing of participants who discontinue vaccination due to related SLE flares (of any severity), as defined in [Appendix G](#) and Section 7.3.3, will also be produced.

### 6.3.3.5 Reasons for vaccination discontinuation and early study termination

The number and percentage of participants who discontinue vaccination and who terminate the study early will be tabulated by reason.

## 6.3.4 Immunogenicity analysis

The primary immunogenicity analysis of the study will be to evaluate the magnitude and breadth of nAb responses and as secondary objective to evaluate immune system activation in individuals with SLE.

### 6.3.4.1 General approach

For the statistical analysis of immunogenicity endpoints, data from enrolled participants will be used regardless of how many injections they received. Additional analyses may be performed, limited to participants who received all scheduled injections per protocol.

Discrete categorical assay endpoints (eg, response rates) will be analyzed by tabulating the frequency of positive response for each assay by antigen at each timepoint for which an assessment is performed. Crude response rates will be presented with their corresponding 95% confidence interval estimates calculated using the exact method (102).

For quantitative assay data (eg, cytokine quantification by Luminex assay), graphical and tabular summaries of the distributions by antigen, timepoint will be made. Additionally, comparisons to controls selected from other studies may be made by treatment group. For all primary and secondary immunogenicity endpoints, box plots and plots of estimated reverse cumulative distribution curves will be used for graphical display.

### 6.3.4.2 Primary analyses of neutralization breadth and magnitude

The area-under-the-magnitude-breadth curve (AUC-MB) to a global panel of isolates (103) will be computed for each participant with evaluable neutralization data, as described in (104). Participant-level AUC-MB may also be computed for the historical controls, ideally based on the same global panel of isolates. The 95% CIs about the mean-differences in AUC-MBs between study cohorts will be reported. Regression models may be used to compare the AUC-MB between study cohorts, accounting for potential confounding factors such as age, gender, or other immune responses etc.

The analyses of magnitude-breadth described above are based on the endpoint area-under-the-curve, which is interpreted as the average  $\log_{10}$  IC50 to the set of isolates in the test panel. Use of this endpoint is maximally statistically powerful if one study cohort has greater magnitude and breadth than the comparator study cohort, but may miss an effect wherein one study cohort has greater magnitude and the comparator has greater breadth. Therefore, a secondary analysis may compare the distribution of magnitude-breadth curves among cohorts using the

test statistic  $\max|B_d^G|$  from Huang, et al (104), which is designed to detect general differences in magnitude-breadth curve distributions.

In addition, the geometric mean titers of Nab responses across a panel of isolates will be computed to determine the presence of bnAbs.

#### 6.3.4.3 Analyses of immune activation

Box plots of systemic cytokines, B and T cell populations, and B and T cell activation will be generated for baseline values and for values measured during the course of the study by visit. Each box plot will show the first quartile, the median, and the third quartile. Outliers (values outside the box plot) will also be plotted.

For each assessment of immune activation, summary statistics will be presented by timepoint, as well as changes from baseline for postenrollment values.

#### 6.3.4.4 Multivariate display of immunogenicity endpoints

Data visualization techniques may be used to explore the relationship among immunogenicity readouts. The set of readouts may be based on one of the primary endpoints (eg, nAb), on the set of primary endpoints, or on immunogenicity endpoints that also include secondary or exploratory endpoints. To understand the relationship between pairs of readouts, scatter plots may be used when the number of readouts is small or for a larger number of readouts, a heatmap showing the degree of correlation between any two pairs. Principal component analysis (PCA) and associated ‘biplots’ of the scores and loadings are particularly useful to understand associations between readouts, especially when readouts are correlated.

### 6.3.5 Analyses prior to end of scheduled follow-up visits

Any analyses conducted prior to the end of the scheduled follow-up visits should not compromise the integrity of the trial in terms of participant retention or safety or immunogenicity endpoint assessments.

#### 6.3.5.1 Safety

During the course of the trial, safety data will be prepared approximately every 4 months for review by the SMB. Ad hoc safety reports may also be prepared for SMB review at the request of the HVTN 121 PSRT.

#### 6.3.5.2 Immunogenicity analyses

This is an open label vaccine study for which immunogenicity, as measured by neutralization GMT against a standard panel of HIV-1 pseudoviruses, is a primary endpoint of the study. In addition, there are immunogenicity secondary endpoints, and statistical analysis of the secondary immunogenicity endpoint(s) may be performed during the course of the study. Every effort will be made to reduce bias

by not performing early analysis of samples from this study. Where possible, analyses of these secondary endpoints will be performed when all participants have completed the corresponding final immunogenicity visit and data are available for analysis from at least 80% of these participants.

The Laboratory Program will review the analysis report prior to distribution to the protocol chairs, DAIDS, study product developer, and other key HVTN members and investigators. Reports for distribution or presentation should use pubIDs and not PTIDS for individual responses. Distribution of reports will be limited to those with a need to know for the purpose of informing future trial-related decisions. The HVTN leadership must approve any other requests for HVTN immunogenicity analyses prior to the end of the scheduled follow-up visits.

## 7 Selection and withdrawal of participants

Participants will be low-risk, HIV-uninfected (seronegative) adults, who have been diagnosed with SLE, who comprehend the purpose of the study and have provided written informed consent. Potentially eligible participants will be identified in collaboration with rheumatology clinic(s) and through community advertising, and will then be screened by an initial interview. Volunteers will be recruited and screened; those determined to be eligible, based on the inclusion and exclusion criteria, will be enrolled in the study. Final eligibility determination will depend on results of laboratory tests, medical history, physical examinations, answers to self-administered and/or interview questions and review of medical records as appropriate.

Investigators should always use good clinical judgment in considering a volunteer's overall fitness for trial participation. Some volunteers may not be appropriate for enrollment even if they meet all inclusion/exclusion criteria. Medical, psychiatric, occupational, or other conditions may make evaluation of safety and/or immunogenicity difficult, and some volunteers may be poor candidates for retention.

Determination of eligibility, taking into account all inclusion and exclusion criteria, must be made within 28 days prior to enrollment unless otherwise noted in Sections 7.1 and 7.2.

### 7.1 Inclusion criteria

#### General and Demographic Criteria

1. **Age** of 18 to 50 years
2. **Weight** > 110 pounds
3. Meets **ACR criteria for the classification of SLE** (86, 87, 105) with serologic evidence of disease including a positive test for antinuclear antibodies at a titer of 1:640 or greater, or the presence of a positive test for antibodies to dsDNA, or the presence of anti-Sm, anti-RNP, or anti-Ro antibodies, as documented by medical records and as assessed by a rheumatologist or designee.
4. Currently taking hydroxychloroquine for SLE and for at least 6 months prior to enrollment
5. **Access to a participating HVTN CRS** and willingness to be followed for the planned duration of the study
6. Ability and willingness to provide **informed consent**

7. **Allows ongoing access to medical records pertaining to their rheumatologic disease**
8. **Assessment of understanding:** volunteer demonstrates understanding of this study; completes a questionnaire prior to first vaccination with verbal demonstration of understanding of all questionnaire items answered incorrectly
9. **Agrees not to enroll in another study** of an investigational research agent before the last required protocol clinic visit

